## 1 GLOSSARY OF TERMS

Names of test product(s)	Throughout this document, test product(s) will be referred to as TFNT20
Name of Control Product(s)	N/A
Adverse Device Effect (ADE)	Adverse event related to the use of an investigational medical device (test product) or control product. Note: This definition includes adverse events resulting from insufficient or inadequate instructions for use, deployment, implantation, installation, or operation; any malfunction; and use error or intentional misuse of the test product or control product.
Adverse Event (AE)	
Any untoward medical occurrence, unintended disease or injury, or untoward clinical signs (including abnormal laboratory findings) in subjects, users or other persons, whether or not related to the investigational medical device (test product). Note: For subjects, this definition includes events related to the test product, the control product, or the procedures involved. For users or other persons, this definition is restricted to events related to the test product.
 
Requirements for reporting Adverse Events in the study can be found in Section 11.

Anticipated Serious Adverse Device Effect (ASADE)	Serious adverse device effect which by its nature, incidence, severity, or outcome has been identified in the risk management file.
Device Deficiency	
Inadequacy of a medical device with respect to its identity, quality, durability, reliability, safety, or performance. Note: This definition includes malfunctions, use errors, and inadequate labeling.
 
Requirements for reporting Device Deficiencies in the study can be found in Section 11.

Enrolled Subject	Any subject who signs an informed consent form for participation in the study.

Investigational Product	Is defined as a preventative (vaccine), a therapeutic (drug or biologic), device, diagnostic, or palliative used as a test or control product in a clinical trial, including a product with a marketing authorization when used or assembled (formulated or packaged) in a way different from the authorized form, or when used for an unauthorized indication, or when used to gain further information about the authorized form.
Malfunction	Failure of a medical device to perform in accordance with its intended purpose when used in accordance with the instructions for use or clinical investigation plan.
Non-serious Adverse Event	Adverse event that does not meet the criteria for a serious adverse event.
Serious Adverse Device Effect (SADE)	Adverse device effect that has resulted in any of the consequences characteristic of a serious adverse event.
Serious Adverse Event (SAE)	Adverse event that led to any of the following: 

• Death.

• A serious deterioration in the health of the subject that either resulted in:

a. a life-threatening illness or injury. Note: Life-threatening means that the individual was at immediate risk of death from the event as it occurred, ie, it does not include an event which hypothetically might have caused death had it occurred in a more severe form.

b. any potentially sight-threatening event or permanent impairment to a body structure or a body function.

	
c. in-patient hospitalization or prolonged hospitalization. Note: Planned hospitalization for a pre-existing condition, without serious deterioration in health, is not considered a serious adverse event. In general, hospitalization signifies that the individual remained at the hospital or emergency ward for observation and/or treatment (usually involving an overnight stay) that would not have been appropriate in the physician's office or an out-patient setting. Complications that occur during hospitalization are adverse events. If a complication prolongs hospitalization or fulfills any other serious criteria, the event is serious. When in doubt as to whether "hospitalization" occurred, the event should be considered serious.
 
d. a medical or surgical intervention to prevent a), b) or any ocular secondary surgical intervention excluding posterior capsulotomy”.]
 
e. any indirect harm as a consequence of incorrect diagnostic test results when used within manufacturer’s instructions for use.
 
 
• Fetal distress, fetal death, or a congenital abnormality or birth defect.
 
 
Refer to Section 11 for additional SAEs.

Unanticipated Serious Adverse Device Effect (USADE)
	
Serious adverse device effect which by its nature, incidence, severity or outcome has not been identified in Investigator’s Brochure.


Use Error
	
Act or omission of an act that results in a different medical device response than intended by manufacturer or expected by user. Note: This definition includes slips, lapses, and mistakes. An unexpected physiological response of the subject does not in itself constitute a use error.

## 2 LIST OF ACRONYMS AND ABBREVIATIONS

**Table 2–1 List of Acronyms and Abbreviations Used in This Protocol**

Abbreviation	Definition
ADE	Adverse device effect
AE	Adverse event
ARMD	Age-related macular degeneration
cd	Candela
CI	Confidence interval
CRF	Case report form
D	Diopter(s)
GCP	Good Clinical Practice
IB	Investigator’s brochure
ICF	Informed consent form
IOL	Intraocular lens
IOP	Intraocular pressure
IP	Investigational product
IRB	Investigational review board
LASIK	Laser-assisted in situ keratomileusis
LRI	Limbal relaxing incision
mm	millimeter
MOP	Manual of procedures
PCO	Posterior capsule opacification
PRK	Photorefractive keratectomy
SAE	Serious adverse event
SADE	Serious adverse device effect
SD	Standard deviation
SOP	Standard operating procedure
SSI	Secondary Surgical Intervention(s)
VA	Visual acuity
YAG	Yttrium aluminum garnet laser

### 3 PROTOCOL SUMMARY

This study is a prospective, single-center and non-comparative study. The study will include subjects must be  $\geq 20$  years of age with cataract who would be eligible to receive a TFNT20 lens in at least one eye based on a new Alcon Toric calculator that incorporates ocular trends in Toric IOL planning. Subject with no ocular pathology that could confound study outcome, must require clear cornea cataract extraction, and must desire an IOL that provides the potential for near, intermediate and distance vision and corrects astigmatism. Potential subjects will be screened for enrollment into this clinical trial. Those qualifying will attend a total 5 visits. If the investigational products will be implanted to both eye, the maximum number of visits is total 9 visits. Primary endpoint data will be collected at the final visit, Visit3/3A (30-60 days post implantation). No interim analysis is planned.

Investigational product type	Device
Study type	Interventional
Investigational products	Test Product: AcrySof IQ PanOptix Toric Intraocular Lens Model TFNT20 (hereinafter called "TFNT20")  Control Product: Not applicable
Purpose and rationale	The purpose of this study is to evaluate effectiveness and safety of the TFNT20 when implanted to replace the natural lens following cataract removal. ■ this is intended to confirm the safety of the test product and examine its effectiveness as a Toric lens by examining the subject's astigmatism power.
Objective(s)	To evaluate effectiveness and safety of the TFNT20 when implanted to replace the natural lens following cataract removal.
Endpoint(s)	Primary Effectiveness 
 
Percentage of eyes with <math>\leq 0.25</math> D refractive cylinder at Visit 3/3A (Day 30-60)
 
 Secondary Effectiveness 
 
Percentage of eyes with <math>\leq 0.5</math> D refractive cylinder at Visit 3/3A (Day 30-60)
 

	

• Average manifest refractive cylinder at Visit 3/3A (Day 30-60)

 
[REDACTED]
 

■ [REDACTED]

■ [REDACTED]

■ [REDACTED]

■ [REDACTED]

■ [REDACTED]

 
Safety
 

• Adverse events including SSI

• Device deficiencies

• Posterior capsular opacification

• Posterior capsulotomy

• IOL position change (tilt and decentration)

• Intraocular pressure

• Surgical problems

• Slit Lamp Examination

• Dilated Fundus Examination

• IOL Observations

Assessment(s)
	
[REDACTED]
 

■ [REDACTED]

■ [REDACTED]

■ [REDACTED]

■ [REDACTED]

■ [REDACTED]

 
Safety
 

• Adverse events including SSI

	
 
• History of anterior segment (corneal, anterior chamber, sulcus) or posterior segment (uveal, vitreo-retinal) pathology including retinal vascular occlusive disease, retinal detachment or peripheral retinal laser photocoagulation, ARMD, glaucoma (uncontrolled or controlled with medication) or ocular hypertension, diabetic retinopathy, retinitis pigmentosa and any optic nerve pathology.
 
• History of previous intraocular or corneal (refractive or trauma related) surgery.
 
• Any other planned ocular surgical procedures including but not limited to limbal relaxing incision (LRI)/Astigmatic Keratotomy and LASIK
 


Data analysis and sample size justification
	
To enroll more than or equal to 30 eligible T2 eyes used for analysis, at least 30 subjects will be evaluated by a new Alcon Toric calculator that incorporates ocular trends in Toric IOL planning and unilaterally or bilaterally implanted with the AcrySof IQ PanOptix IOL (TFNT20).
 
Using a new Alcon calculator that incorporates ocular trends in Toric IOL planning, percentage of eyes with <math>\leq 0.25</math> D refractive cylinder at Visit 3/3A (Day 30-60) in T2 group was estimated as 60.9% based on a previous [REDACTED] (T2) study conducted in US. Using the same calculator, the percentage in T0 group was recalculated as 29.2% from the combined result of studies (non-Toric (T0) lenses) conducted in Japan [REDACTED].
 
[REDACTED] Statistical test will be conducted to compare percentage of T2 with a constant of 29.2% as percentage of T0. With 30 eyes from 30 subjects in T2 group, assuming the percentage of T2 is equal to 60.9% [REDACTED] the statistical power to demonstrate superiority of T2 to T0 is 91.6% with one-sided alpha of 2.5%, using an exact test of binomial proportion.

Anticipated study period
	
Sep, 2020 ~ Sep, 2021

Key words
	
Cataract, intraocular lens, Toric, astigmatism

Associated materials
	
Not applicable.

**Table 3-1 Schedule of Study Procedures and Assessments**

Activity	Visit 0/0A (Day-60 to 0)	Visit 00/00A (Day 0)	Visit 1/1A (Day 1-2)	Visit 2/2A (Day 7-14)	Visit 3/3A (Day 30-60)
Informed Consent*	X				
Demographics	X				
Medical History	X	X			
Concomitant Medications	X	X	X	X	X
Urine Pregnancy Test**	X (Visit 0 only)				
Inclusion/Exclusion	X	X			
██████████	■		■	■	■
██████████	■		■	■	■
██████████	■		■	■	■
██████████	■		■	■	■
Subjective Manifest Refraction	X		X	X	X
Slit-Lamp Examination	X		X	X	X
Fundus exam with dilated pupil	X				X
Keratometry	X		(X)	(X)	X
Target Residual Refractive Error	X				
Calculation by new Alcon Toric calculator that incorporates ocular trends in Toric IOL planning	X				
Topography	X		(X)	(X)	X
Axial Length	X		(X)	(X)	X
Anterior chamber depth	X		(X)	(X)	X
Intraocular Pressure	X		X	X	X
██████████		■	■		■
██████████					
Operation Record****		X			
Posterior capsular opacification			X	X	X
Posterior capsulotomy			X	X	X
IOL observations		X	X	X	X
IOL position change (tilt an decentration)			X	X	X
Adverse Events	X	X	X	X	X
Secondary Surgical Intervention		X	X	X	X
Device Deficiencies	X	X	X	X	X

(X): The data will be captured if the investigator judged to be able to conduct the examination based on the subject's condition.

\* When a subject receives the bilateral study lens implantation, written informed consent form prior to the examinations at Visit 0A is needed.

\*\* Women of child-bearing potential only

\*\*\* A slit lamp photograph shall be recorded and kept as a source document.

\*\*\*\* Operative eye, lens information, final incision size, surgical problems and other surgical procedures during surgery will be collected.

## 4 PROTOCOL AMENDMENTS

Modification of the protocol is prohibited without prior written agreement in the form of a protocol amendment. All amendments must be created by the Study Sponsor and must be approved by the IRB and global and regional Health Authorities, as applicable, prior to implementation except when required to mitigate immediate safety risks or when the changes involve only logistical or administrative revisions.

Amendments may necessitate that the informed consent and other study-related material be revised. If the consent form is revised, all subjects currently enrolled in the study must sign the approved, revised informed consent (re-consent), as required by the IRB.

[REDACTED]

## 5 INTRODUCTION

### 5.1 Rationale and Background

The first clinical results of the multifocal intraocular lenses were reported in the United States in 1987. The first Japanese clinical study was performed and reported in the early 1990's. In general, multifocal intraocular lenses are roughly divided into diffractive and refractive types. Diffractive lenses are structured to separate incident light energy to far and near visions, while refractive lenses have an optical zone structure consisting of far and near vision zones arranged in an alternate, concentric manner. Since the diffractive multifocal intraocular lens product, "Alcon® AcrySof® ReSTOR® Single Piece" (medical device approval number: 21900BZX00605000, Alcon Japan Ltd.) was first approved in 2007, various multifocal intraocular lenses have been developed in Japan. As opposed to monofocal intraocular lenses, intraocular lenses with 2 or more focuses are collectively called multifocal intraocular lenses. Actually bifocal intraocular lenses focusing on far and intermediate or near objects account for most of multifocal intraocular lenses in Japan, however three trifocal intraocular lenses, "Alcon Acrysof IQ PanOptix Single Piece (medical device approval number: 23100BZX00042000, Alcon Japan Ltd.)" and "Alcon Acrysof IQ PanOptix Toric Single Piece (medical device approval number: 23100BZX00043000, Alcon Japan Ltd.)", focusing on far, intermediate, and near objects were approved in 2019.

The AcrySof IQ PanOptix Toric IOL is a diffractive multifocal lens with a toric optic to correct pre-existing corneal astigmatism. The ACRYSOF IQ PanOptix Toric IOL is commercially available in 4 cylinder powers to reduce pre-existing corneal astigmatism (ACRYSOF IQ PanOptix Toric IOL TFNT30 - TFNT60), but the TFNT20, having lower cylinder power than approved products, has not been approved.

Levels of astigmatism 0.5 D to 1.0 D are estimated to represent 35.6% of all cataract cases in Japan. For those patients, a lack of astigmatism correction can limit their desired outcome of visual acuity. Correcting astigmatism concurrently during phacoemulsification cataract surgery eliminates the need for additional surgical procedures, such as excimer laser keratectomy and limbal and corneal relaxing incision techniques. For example, the excimer laser can be cost prohibitive and limbal and corneal relaxation incision can have less predictable results compared to Toric IOL options.

The effect of astigmatism on the visual acuity of a multifocal intraocular lens implanted eyes are greater than that of a monofocal intraocular lens, and in particular, reduction of postoperative residual astigmatism is desired for multifocal intraocular lenses. Therefore, even if the cylinder power is low, it is important to reduce cylinder power astigmatism.

The TFNT20, a multifocal IOL with an adequate cylinder power for low cylinder power astigmatism patients, will provide patients, as an additional treatment option, with post-cataract surgery quality of vision as they wish for, and is expected to contribute to the improved quality of vision after cataract surgery.

## 5.2 Purpose of the Study

The purpose of this study is to evaluate effectiveness and safety of the TFNT20 when implanted to replace the natural lens following cataract removal. So this is intended to confirm the safety of the test product and examine its effectiveness as a Toric lens by examining the subject's astigmatism power.

At the end of the study, a clinical study report will be prepared in accordance with applicable regulatory requirements and standards.

## 5.3 Risks and Benefits

[REDACTED]

The TFNT20, a multifocal IOL with an adequate cylinder power for low cylinder power astigmatism patients, is expected to contribute to the improved quality of vision after cataract surgery.

There may also be unknown risks to use of test product. Any risk to subjects in this clinical study will be minimized by compliance with the eligibility criteria and study procedures, clinical oversight and monitoring.

## 6 STUDY OBJECTIVES

### 6.1 Primary Objective(s)

[figure not shown]
**Table 6-1 Primary Endpoint(s)**

[figure not shown]
Objective(s)	Endpoint(s)
To evaluate primary effectiveness of the TFNT20 when implanted to replace the natural lens following cataract removal.	

Percentage of eyes with <math>\leq 0.25</math> D refractive cylinder at Visit 3/3A (Day 30-60)

### 6.2 Secondary Endpoint(s)

**Table 6-2 Secondary Endpoint(s)**

Objective(s)	Endpoint(s)
To evaluate secondary effectiveness of the TFNT20 when implanted to replace the natural lens following cataract removal.	

Percentage of eyes with <math>\leq 0.5</math> D refractive cylinder at Visit 3/3A (Day 30-60)

Average manifest refractive cylinder at Visit 3/3A (Day 30-60)

## 6.5 Safety Objective(s)

**Table 6–4 Safety Endpoint(s)**

Objective(s)	Endpoint(s)
To evaluate safety of the TFNT20 when implanted to replace the natural lens following cataract removal.	

• Adverse events including SSI

• Device deficiencies

• Posterior capsular opacification

• Posterior capsulotomy

• IOL position change (tilt and decentration)

• Intraocular pressure

• Surgical problems

• Slit Lamp Examination

• Dilated Fundus Examination

• IOL Observations

[figure not shown]
## **7 INVESTIGATIONAL PLAN**

### **7.1 Study Design**

This study is a prospective, single-center and non-comparative study. The study will include subjects must be  $\geq 20$  years of age with cataract who would be eligible to receive a TFNT20 lens in at least one eye based on a new Alcon Toric calculator that incorporates ocular trends in Toric IOL planning. Subject with no ocular pathology that could confound study outcome, must require clear cornea cataract extraction, and must desire an IOL that provides the potential for near, intermediate and distance vision and corrects astigmatism. Potential subjects will be screened for enrollment into this clinical trial. Those qualifying will attend a total 5 visits, 1 is preoperative, 1 is operative and 3 are postoperative visits. If the test products will be implanted to both eye, the maximum number of visits is 9 visits, 1 is preoperative, 2 are operative and 6 are postoperative visits. Unscheduled visits may be attended if needed for medical attention.

An overview of the study design is depicted in Figure 7-1.

**Figure .7-1 Study Design**

## **7.2 Rationale for Study Design**

The purpose of this clinical study is to evaluate effectiveness and safety of the TFNT20 when implanted to replace the natural lens following cataract removal in at least one eye based on a new Alcon Toric calculator that incorporates ocular trends in Toric IOL planning.

### **7.2.1 Purpose and Timing of Interim Analyses and Resulting Design Adaptations**

Not applicable.

## **7.3 Rationale for Duration of Treatment/Follow-Up**

Follow-up period required to properly evaluate effectiveness of astigmatism reduction of IP are set up.

## **7.4 Data Monitoring Committee**

Not applicable

## 8 STUDY POPULATION

The study population includes approximately 30 subjects to be enrolled at 1 site.

To participate in the clinical trial, subjects must be  $\geq 20$  years of age with cataract who would be eligible to receive a TFNT20 lens in at least one eye based on a new Alcon Toric calculator that incorporates ocular trends in Toric IOL planning. Subject with no ocular pathology that could confound study outcome, must require clear cornea cataract extraction, and must desire an IOL that provides the potential for near, intermediate and distance vision and corrects astigmatism. Additional entry criteria are listed below in Sections 8.1 through 8.3.

Check all entry criteria at baseline (Visit 0/0A) and at both surgical visits (Visit 00/00A).

If the implantation was aborted and the IOL did **not** touch the eye, then the subject is required to discontinue from the study and standard of care for IOL implantation is followed. Refer to Section 10.3 Discontinued Subjects for further details. If the implantation was aborted and the IOL did touch the eye, then the subject is followed for safety evaluation on this eye only.

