### 8.1 Inclusion Criteria

Written informed consent must be obtained before any study specific assessment is performed. Upon signing informed consent, the subject is considered enrolled in the study.

Subjects eligible for inclusion in this study must fulfill **all** of the following criteria: Among the criteria listed below, ocular criteria relates to the study eye only.

1. Adults, 20 years of age or older at the time of informed consent for participating in this study, of either gender, Japanese patient diagnosed with age-related cataract.
2. Planned routine cataract surgery (need determined by the expert opinion of the investigator).
3. Eligible to be implanted with the TFNT20 as determined by a new Alcon Toric calculator in at least one eye that incorporates ocular trends in surgical planning.
4. To qualify for fellow eye implant with TFNT20, subject must have no clinically significant findings at the Visit 1 examination of the first implanted eye.

Note: This criterion only applies to subjects who are eligible for both eyes and wishes to be implanted into fellow eye with TFNT20.

5. Willing and able to complete all required postoperative visits.
6. Subjects for able to comprehend and sign the informed consent form for participating in this study.  
For the subjects who are eligible for both eyes and wishes to be implanted into fellow eye with TFNT20, subject has to comprehend and sign the informed consent form for the second eye surgery and the study examinations prior to the examinations at Visit 0A.
7. Clear intraocular media other than cataract.
8. Subjects for whom postoperative emmetropia is planned (spherical equivalent  $\pm$  0.50 D).
9. Potential postoperative BCDVA of 0.5 decimal or better.

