## 12.8 Sample Size Justification

To enroll more than or equal to 30 eligible T2 eyes used for analysis, at least 30 subjects will be evaluated by a new Alcon Toric calculator that incorporates ocular trends in Toric IOL planning and unilaterally or bilaterally implanted with the AcrySof IQ PanOptix IOL (TFNT20).

Using a new Alcon calculator that incorporates ocular trends in Toric IOL planning, percentage of eyes with  $\leq 0.25$  D refractive cylinder at Visit 3/3A (Day 30-60) in T2 group was estimated as 60.9% based on a previous [REDACTED] (T2) study conducted in US. Using the same calculator, the percentage in T0 group was recalculated as 29.2% from the combined result of studies (non-Toric T0 lenses) conducted in Japan [REDACTED] [REDACTED]. Statistical test will be conducted to compare percentage of T2 with a constant of 29.2% as percentage of T0. With 30 eyes from 30 subjects in T2 group, assuming the percentage of T2 is equal to 60.9% [REDACTED], the statistical power to demonstrate superiority of T2 to T0 is 91.6% with one-sided alpha of 2.5%, using an exact test of binomial proportion.

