5.4 Interim Analysis for Safety

No interim analysis is planned.

6 Pharmacokinetic Analysis Strategy

Not Applicable.

7 Analysis Strategy for Other Endpoints

Not Applicable.

8 Sample Size and Power Calculations

To enroll more than or equal to 30 eligible T2 eyes used for analysis, at least 30 subjects will be evaluated by a new Alcon Toric calculator and unilaterally or bilaterally implanted with the AcrySof IQ PanOptix IOL (TFNT20).

Using a new Alcon calculator, percentage of eyes with ≤ 0.25 D refractive cylinder at Visit 3/3A (Day 30-60) in T2 group was estimated as 60.9% based on a previous [REDACTED] (T2) study conducted in US. Using the same calculator, the percentage in T0 group was recalculated as 29.2% from the combined result of studies (non-Toric T0 lenses) conducted in Japan [REDACTED]. Statistical test will be conducted to compare percentage of T2 with a constant of 29.2% as percentage of T0. With 30 eyes from 30 subjects in T2 group, assuming the percentage of T2 is equal to 60.9% [REDACTED] the statistical power to demonstrate superiority of T2 to T0 is 91.6% with one-sided alpha of 2.5%, using an exact test of binomial proportion.

9 References

No references.

10 Revision History

This is the original (Version 1.0) Statistical Analysis Plan for this study. This version of the Statistical Analysis Plan is based on Version 2.0 of the study protocol.

Signature Page for V-CLN-0002915 v1.0

Signature Page for V-CLN-0002915 v1.0

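### Does planning for about 30 consented subjects undercut a 91.6% power figure that assumes 30 analysed subjects?

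*Protocol*

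**What the plan says.** Protocol Section 8 describes the size of the study in one sentence: "The study population includes approximately 30 subjects to be enrolled at 1 site". The glossary defines an enrolled subject as "Any subject who signs an informed consent form for participation in the study", and Section 8.1 agrees: "Upon signing informed consent, the subject is considered enrolled in the study".

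The sample size text uses a different count. Section 12.8 opens "To enroll more than or equal to 30 eligible T2 eyes used for analysis, at least 30 subjects will be evaluated" with the sponsor's calculator, and adds that these subjects are "unilaterally or bilaterally implanted with the AcrySof IQ PanOptix IOL (TFNT20"). The protocol summary and SAP Section 8 carry the same statement. The power figure of 91.6% is conditioned on one eye per subject; in SAP Section 8, "With 30 eyes from 30 subjects in T2 group".

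Four other provisions bear on the point:

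- Losses after consent are foreseen: screen failure (Section 10.3.1), exclusion during surgery (Sections 8.3 and 10.1.2), aborted implantation (Section 8) and discontinuation (Section 10.3.2).
- The same subject may not be screened again (Section 8.4).
- Missing data are not imputed (Section 12.5; observed data only in SAP Table 4-1).
- Both eyes of a bilaterally implanted subject enter the primary analysis (Section 12.4.1.2; SAP Section 4.3).

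**The concern.** The number 30 appears to do three jobs: subjects who consent, subjects who are implanted, and subjects who contribute to the primary test. These counts agree only if nobody is lost in between, yet the protocol itself lists several routes to loss and neither document states an allowance. A site that took Section 8 as its recruitment limit would stop at about 30 signatures and deliver fewer independent subjects than the power statement assumes. Second eyes would raise the number of eyes but not the number of subjects. In a small single-arm study that rests on one test, the cost would be a lower chance of showing superiority over the historical 29.2%, and two passages that imply different points at which to stop recruiting.

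**Working it through.** **Inputs.** Null proportion 0.292, alternative 0.609, one-sided alpha 0.025, exact binomial test, 30 eyes from 30 subjects (Protocol Sections 12.4.1.1 and 12.8; SAP Sections 4.2 and 8). Neither document gives a loss rate, so every rate d below is an assumption.

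**Step 1: reproduce the stated power.** The critical count k is the smallest value with P(Bin(n, 0.292) ≥ k) ≤ 0.025. Power is P(Bin(n, 0.609) ≥ k). For n = 30, k = 15, the attained alpha is 0.0131 and power is 0.9195. That is 0.35 percentage points above the stated 91.6%, a gap that rounding of the two input rates or redacted detail could explain. The figure is sound for the design in Section 12.8.

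**Step 2: power with fewer evaluable subjects, one eye each.**

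| n | k | attained alpha | power |
|---|---|---|---|
| 30 | 15 | 0.0131 | 0.9195 |
| 29 | 14 | 0.0232 | 0.9418 |
| 28 | 14 | 0.0163 | 0.9142 |
| 27 | 14 | 0.0111 | 0.8764 |
| 26 | 13 | 0.0204 | 0.9086 |
| 25 | 13 | 0.0138 | 0.8675 |
| 24 | 13 | 0.0090 | 0.8127 |
| 23 | 12 | 0.0173 | 0.8577 |
| 22 | 12 | 0.0112 | 0.7977 |

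The sequence is not monotone, because k moves in whole steps. Power is higher at 26 than at 27, and higher at 23 than at 24. The values 87.6% (27 subjects, 10% loss) and 81.3% (24 subjects, 20% loss) are local low points. Read alone, they overstate the cost of attrition.

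**Step 3: average over the uncertain number lost.** Suppose 30 subjects consent and each independently reaches analysis with probability 1 − d. Expected power is the sum over m of P(Bin(30, 1 − d) = m) × power(m).

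| assumed d | expected power |
|---|---|
| 0% | 91.9% |
| 5% | 91.9% |
| 10% | 89.7% |
| 15% | 87.3% |
| 20% | 84.8% |
| 30% | 79.4% |

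Against the stated 91.6%, a 10% loss costs 91.6 − 89.7 = 1.9 points and a 20% loss costs 91.6 − 84.8 = 6.8 points.

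**Step 4: what second eyes add.** With m subjects, a bilateral share b and within-subject correlation ρ, the number of eyes is m(1 + b). The effective number of independent eyes is [m(1 + b)]² / [m(1 − b) + mb(2 + 2ρ)]. For m = 24 and b = 0.25 there are 30 eyes:

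- ρ = 0.3: 900 / (18 + 6 × 2.6) = 900 / 33.6 = 26.8
- ρ = 0.8: 900 / (18 + 6 × 3.6) = 900 / 39.6 = 22.7

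So second eyes can restore the eye count, but they recover the lost information only in part, and at high correlation not at all. Both b and ρ are assumed.

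**Step 5: which passage governs recruitment.** Section 8 uses an approximate number and contains no limit or stopping rule. The target stated as a minimum, covering implantation as well as evaluation, stands in the protocol summary, Section 12.8 and SAP Section 8. The ban in Section 8.4 concerns screening the same person twice. It does not prevent new subjects from replacing those lost. A reader of the whole protocol would recruit until the minimum is met, and Steps 2 to 4 then have no bearing on screen failures or on eyes excluded at surgery.

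**The case for a change.** The best counter-argument is that the contradiction needs no assumption. By the protocol's own glossary, about 30 enrolled means about 30 consents, and a tolerance around 30 consents does not turn consents into implants. If each subject has an assumed 5% chance of loss, all 30 reach analysis with probability 0.95³⁰ = 21%; at 10% it is 0.90³⁰ = 4%. Routine tests come before consent (Section 10.1.1), which removes some ineligible patients early, but exclusions during surgery and missed final visits come later regardless. Second eyes do not supply the missing independent subjects.

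The wording mismatch and the absence of a stated allowance both stand. The step from there to a power problem does not. The chance that all 30 subjects survive to analysis is the wrong yardstick, since losing one or two leaves power at 94.2% or 91.4%, and losing four leaves 90.9%. The 30 eyes from 30 subjects is the condition under which power was computed; the stated recruitment aim is at least 30 eligible eyes, from at least 30 implanted subjects.

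Restating power for 27 subjects would also be no improvement. It would replace a figure that can be reproduced with one that rests on an undocumented 10% loss and falls on a low point of the curve. If Section 8 really were a limit, the answer would be more consents, 30/(1 − d) rounded up: 32 at 5% and 34 at 10%. The existing minimum already allows that.

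**Conclusion.** No change to the plan is called for. Section 8 uses the word enrolled more loosely than the glossary does, and the minimum stated in Section 12.8, the protocol summary and SAP Section 8 settles what the site must deliver. Bringing that one sentence into line would be harmless editing and would affect no analysis, result or conclusion.

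The stated 91.6% is delivered by the Section 12.8 design (91.95% on recomputation). Even on the unfavourable reading, with recruitment ended at 30 consents and no credit for second eyes, expected power stays near 90% at an assumed 10% loss and near 85% at 20%. It drops below 80% only when the assumed loss approaches 30%. These figures take the plan's 60.9% alternative as given, count one eye per subject, and treat losses as independent of outcome. Whether the exact test is suitable when both eyes of a subject are analysed is a separate question and is not decided here.
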